Title	Scorpio NRG[®] prospective, open-label, post-market international multicentre outcome Study
Protocol Number	K-S-002 (previous protocol number SLCRG-001-2007)
Phase	Post-marketing
Sponsor	Stryker Orthopaedics Mahwah, USA
Study design	Prospective, open-label, international
Study Duration	12 months enrolment period + up to a minimum of 5 years follow-up for each case = ~ 6 years total duration.
Study Centre(s)	5
Objectives	To collect basic function and patient satisfaction data for observation and analysis. Specific objectives include the following: Evaluate the effect of component design on functional performance by comparing postoperative Knee Society Scores with preoperative. Evaluate the effect of component design on patient activity by comparing postoperative Lower Extremity Activity Scale (LEAS) with preoperative. Evaluate patient satisfaction using SF-36 [®] Health Survey. Evaluate quality of life using Knee Injury and Osteoarthritis Outcome Score (KOOS) and EuroQol 5D (EQ-5D).
Primary endpoint	Survival (revision rate)
Indication	Primary total knee replacement
Study device / control device	Scorpio NRG [®] Total Knee System
Number of Subjects	250 Patients (Competitive recruitment)


Inclusion and Exclusion Criteria
	
Inclusions:
 
 1) Patient is able to understand the meaning of the study and is willing to sign the EC approved, study specific Informed Patient Consent Form. 2) The subject is a male or non-pregnant female between 40 and 75 years of age. 3) The subject requires a primary total knee replacement. 4) Patients with osteoarthritis or posttraumatic arthritis (no rheumatoid arthritis) 5) The subject has intact collateral ligaments. 6) The subject is willing and able to comply with postoperative scheduled clinical and radiographic evaluations and rehabilitation. 7) The subject is capable of understanding the patient scores in the national language. 
Exclusions:
 
 1) The subject is morbidly obese, defined as Body Mass Index (BMI) of > 40. 2) The subject has a history of total or unicompartamental reconstruction of the affected joint. 3) The subject will be operated bilaterally. 4) Patients who had a Total Hip Arthroplasty (THA) on contralateral and/or ipsilateral side within the last year that is considered to have an unsatisfactory outcome (Patients with contralateral and/or ipsilateral THA > 1 year ago with good outcome can be included in the study). 5) Patients who had a Total Knee Arthroplasty (TKA) on contralateral side within the last year that is considered to have an unsatisfactory outcome. (Patients with contralateral TKA > 1 year ago with good outcome can be included in the study). 6) Patients who will need lower limb joint replacement for another joint within one year. 7) The subject has had a high tibial osteotomy or femoral osteotomy. 8) The subject has a neuromuscular or neurosensory deficiency, which would limit the ability to assess the performance of the device. 9) The subject has a systemic or metabolic disorder leading to progressive bone deterioration. 10) The subject is immunologically suppressed or receiving steroids in excess of normal physiological requirements. 11) The subject's bone stock in compromised by disease or infection which cannot provide adequate support and/or fixation to the prosthesis. 12) The subject has had a knee fusion to the affected joint. 13) The subject has an active or suspected latent infection in or about the knee joint. 14) Proven or suspected hypersensitivity to one or more than one of the device materials. 15) Female patients planning a pregnancy during the course of the study. 16) The subject is a prisoner. 17) Severe deformities: varus/valgus deformity >10° (mech. axis), bowed femur >20°, flexion contracture >10°
---	---

Patient evaluations will be performed according to the schedule below:

Table 1 – Evaluation schedule

Evaluation	Pre-OP	Intra-OP	Prior to discharge	3 months (± 3 weeks)	1 year (± 2 months)	3 years (± 2 months)	5 years (± 3 months)	7 years** (± 3 months)
Demographics	x							
Medical history	x							
Clinical evaluation	x		x	x	x	x	x	x
Surgical details		x						
KSS	x			x	x	x	x	x
Lower Extremity Activity Scale	x			x	x	x	x	x
KOOS	x				x		x	x
SF-36	x			x	x	x	x	x
EQ-5D	x			x	x	x	x	x
*Radiographs: ap, lateral	x		x		x		x**	x
*Radiograph: merchant view	x			x				
*Radiograph: long leg	x			x				

*Radiographs will not go into analysis

**optional

CLINICAL PROTOCOL PLAN SIGNATURE PAGE

TITLE: **Scorpio NRG® prospective, open-label, post-market international multicentre outcome Study.**

Protocol #: K-S-002

Version Date: 2nd Amendment, Version 1.3 2019JAN09

Prepared by:  2019FEB18 [name] Clinical Study Manager Stryker Orthopaedics - Joint Replacement Clinical Operations
	
I confirm correctness of my signature from 2019FEB18

Approved by:  19FEB2018 19FEB2019 [name] Manager, Clinical Research Stryker Orthopaedics - Joint Replacement Clinical Operations
	
I confirm correct ness of my signature from 2019Feb19

 19FEB2019 [name] Sr. Director Clinical Operations Stryker Orthopaedics - Joint Replacement Clinical Operations
	
I confirm correctness of my signature from 2019FEB19

CONTACT INFORMATION

Study Sponsor: Stryker Orthopaedics
[name]
[name]
USA

Contact: **[name]**
Clinical Study Manager
Stryker GmbH & Co KG
[name]
[name]
Germany

[contact]
[contact]

[name]
Manager, Clinical Research
Orthopaedics – Joint Replacement
[name]
[name]
USA

[contact]
[contact]
[contact]
[contact]

1. Preliminary Investigations and Justification of the Study

This document is a protocol for a clinical investigation. This clinical investigation will be conducted in compliance with this protocol, ISO 14155-GCP, and the applicable regulatory requirements.

1.1. Background

This document is a protocol for a clinical outcome study. This study will be conducted in compliance with the protocol, Good Clinical Practice Guidelines, associated regulations and all applicable research requirements.

Today total knee joint replacements are routinely implanted with total knee arthroplasty being one of the most successful joint reconstructions. The number of total knee replacements is rising worldwide, and patients are increasingly younger at the time of implantation. The developments of the implant design, as well as the improvement of instruments, over the last decades enable sound and reliable results. With increasing success of joint replacement and decreasing age of patients, the expectations of total knee arthroplasty are constantly on the rise. Patients anticipate reduced painkiller, long lifetime of the implant with high functionality and a great range of motion to carry out daily activities and sports. Apart from regaining a lifestyle without major knee pain, some cultural and religious aspects (e.g. kneeling while praying) where deep flexion is required, are a challenge for modern knee-systems.

The Scorpio NRG[®] Knee System has been designed with these activities in mind. Scorpio NRG[®] has a greater internal and external rotational freedom throughout the full range of motion when compared to other modern knee replacement designs. Traditional insert designs utilize a less functional partial rotary arc, thus limiting the overall kinematic function of the knee. The Scorpio NRG[®] tibial insert's articulating surface uses a Spherical Arc motion in order to realize greater freedom. By combining a single M/L radius and a Spherical Arc, Scorpio NRG[®] allows for greater rotational freedom without restricting the tibio-femoral contact area. Freedom of rotation is one of the most essential factors in the design of a successful total knee replacement, thus allowing the patient's ligaments to govern motion of the knee.

Furthermore, the component design can contribute to patient's activity level by providing joint stability and improved function. While traditional knee implants are designed with several axes of rotation that may create mid-flexion instability during the transition between radii, a single axis and single radius design can provide consistent collateral ligament isometry and stability throughout the range of motion.

In this outcome study of the Scorpio NRG[®] knee system, we expect improvement of a patient's lifestyle and activities. This study evaluates patients for five (optional seven) years post-surgery. The focus of this study is to evaluate the effect of component design on functional performance and the patient's satisfaction. Thus, the Knee Society Score and the SF-36 is used. Further measures being used include the comparative postoperative with preoperative Lower Extremity Activity Scale (LEAS), Knee Injury and Osteoarthritis Outcome Score (KOOS) and EuroQol 5D (EQ-5D) to evaluate the quality of life.

1.2. Device Description

The Scorpio NRG® Knee System has been CE marked in Europe. This evaluation is therefore considered a post marketing assessment.

In this clinical study, all patients will have the femoral, tibial tray and optional patellar components implanted with bone cement. The Scorpio NRG® Femoral component will be available in Cruciate Retaining (CR) style combined with Scorpio NRG® CR Tibial insert, respectively. In all cases the Scorpio NRG® femoral and tibia inserts will be used in combination with the Tibia Baseplate from the Scorpio® Knee System. A patella component from the Scorpio® Knee System is optional. The components are described below.

FEMORAL COMPONENT:

The Scorpio NRG® femoral components are manufactured from cobalt chromium alloy (ASTM F75) and are available in left and right configurations. The interior surface of the components contains a waffle pattern for the cement interface. These components have been designed to mimic the normal femoral condylar geometry. These components employ a single medial lateral radius, which corresponds with the bearing surface of the intended articulating tibial counterpart. This helps to maintain contact between the femoral condyles and the tibial insert surface throughout the range of motion. The femoral components are available in 9 proportional sizes 3, 4, 5, 6, 7, 8, 9, 11 and 13 (see product brochure).

The Scorpio NRG® CR: Intended for use in combination with the Scorpio NRG® cruciate retaining tibial inserts and the Scorpio® Total Knee System patella components.

TIBIAL INSERT:

The tibial insert components are available in CR and PS designs. Both designs are manufactured from ultra-high molecular weight polyethylene (ASTM F648). Highly crosslinked (X3) polyethylene inserts are to be used in all study patients. A proprietary rotary machining process used on the articulating surface of the tibial insert provides for improved rotation of components. In keeping with the design theory, the tibial insert component employs a single medial-lateral radius. The surface incorporates a posteriorly sloping raised tibial eminence. The insert is assembled to the tibial tray component intraoperatively via a locking wire mechanism. The locking wire is manufactured from wrought cobalt chromium alloy (ASTM F90). The inserts are available in five sizes (3, 5, 7, 9, 11). Each size is available in seven thicknesses 8mm, 10mm, 12mm, 15mm, 18mm, 21mm and 24mm.

TIBIAL BASEPLATE:

The cemented Scorpio® Primary Knee System Tibial Baseplate is to be used in all study cases. The baseplate is manufactured from cobalt-chromium alloy. The Scorpio® Primary Tibial Baseplate is neutral in configuration, and is available in eight proportional sizes (3, 4, 5, 6, 7, 9, 11, 13). The undersurface of the tibial tray has a waffle structure and is designed for use with PMMA bone cement. The keel of the tibial tray is designed with normalizations for rotational stability and cement interdigitation.

PATELLAR COMPONENT:

The use of a patellar component is optional. The Scorpio® System Patellar component is manufactured from highly crosslinked (X3) polyethylene and is available with a superior/inferior medialized offset of 1,5mm.

- medialized dome patella
- concentric dome patella
- universal dome patella

INSTRUMENTATION:

No new instruments have been designed for use with the Scorpio NRG[®] System. These components will use the currently existing Scorpio[®] Total Knee System instrumentation. The only exception is the development of the femoral and tibial insert trials that have the same geometry as the implants.

1.3. Clinical Data to Date

As of the interim analysis completed in December 2014, 220 patients were included across 5 centres between May 2009 and December 2013. The mean age, height and weight were 65.3 years, 171.4 cm and 87.9 kg, respectively. All patients received a Scorpio NRG Total Knee System.

The mean assessment and functional components of the Knee Society Score were 57.6 and 61.7 pre-operatively compared to 83.6 and 88.7 at the 1-year follow-up, respectively. Patient scores including the LEAS, KOOS, SF-36 and EQ5D showed an increase between the pre-operative visit and 1-year follow-up visit. There were three prosthesis revisions reported during the first year of follow-up and three patients have decided to withdraw from the trial. This analysis was carried out in the early stages of follow-up, so it is not possible to draw any conclusions about the performance of the prosthesis in this report.

Overall, the patient group showed improved clinical results in early follow-up.

2. Objectives of the Clinical Investigation

The objective of this study is to collect basic function and patient satisfaction data for observation and analysis.

Specific objectives include the following:

- Evaluate the effect of component design on functional performance by comparing postoperative Knee Society Scores with preoperative.
- Evaluate the effect of component design on patient activity by comparing postoperative Lower Lower Extremity Activity Scale (LEAS) with preoperative.
- Evaluate patient satisfaction using SF-36[®] Health Survey.
- Evaluate quality of life using Knee Injury and Osteoarthritis Outcome Score (KOOS) and EuroQol 5D (EQ-5D).

3. Design of the Clinical Investigation

3.1. Study Design

A prospective, open-label design will be employed. The study is international and multicentre.

3.2. Number of Centers

Cases will be enrolled in up to 5 centres in Europe. See also **Appendix 1** Investigator Contact List.

3.3. Number of Subjects

A total of 250 patients will be enrolled in the study. A competitive recruitment system will be used, meaning patients will be enrolled in all sites until the 250 patients have been recruited.

Enrollment into the study will be stopped when the planned number of patients has been reached between all the study sites (a competitive recruitment system). In the ideal case, this is 50 patients per centre; however, there is no minimum and no maximum number of study patients per site.

3.4. Estimated Study Duration

The enrolment period is estimated to be 12 months. Cases will be evaluated as per the evaluation schedule (Table 1) with follow-up up to a minimum of five years, giving total study duration of approximately six years minimum.

Subjects will be evaluated preoperatively and at follow-up intervals of three months, six months, one year, three years, five years and an optional seven years.

4. Eligibility

The following criteria will be used to distinguish patients eligible for enrolment into this study.

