5.5. Supplies/Device Accountability

The study devices must be stored and handled in accordance with the manufacturer's guidelines. The Investigator will also keep accurate records of the devices assigned to each subject.

The investigator will be asked to attach the labels (with the lot device number), where possible, of the implanted devices to the corresponding patient CRF page in order to keep a tracking of the devices.

6. Evaluations

Subjects will be evaluated preoperatively and at follow-up intervals of three months, one year, three years, five years and an optional seven years (see Tables 1 and 2). Each subject will be followed for a minimum of five years post-implantation. All subject evaluations will be documented by completion of appropriate Case Report Forms.

Table 2 – Evaluation schedule (functional and patient assessment)

Evaluation	Pre-OP	Intra-OP	Prior to discharge	3 months (± 3 weeks)	1 year (± 2 months)	3 years (± 2 months)	5 years (± 3 months)	7 years** (± 3 months)
Demographics	x							
Medical history	x							
Clinical evaluation	x		x	x	x	x	x	x
Surgical details		x						
KSS	x			x	x	x	x	x
Lower Extremity Activity Scale	x			x	x	x	x	x
KOOS	x				x		x	x
SF-36	x			x	x	x	x	x
EQ-5D	x			x	x	x	x	x
*Radiographs: ap, lateral	x		x		x		x**	x
*Radiograph: merchant view	x			x				
*Radiograph: long leg	x			x				

*Radiographs will not go into analysis

**optional

Basic demographic and medical history information are to be collected at the most two months prior to surgery. This information includes age and gender. Height, weight, primary diagnosis, concurrent medical condition and prior treatment to the affected joint are also documented at this time.

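### Do the outdated enrolment and duration figures, and a six-month visit listed only in Section 3.4, call for a change to the plan?

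*Combined protocol and SAP*

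**What the plan says.** Section 3.3 sets the size: "A total of 250 patients will be enrolled in the study". Recruitment is competitive, so that "patients will be enrolled in all sites until the 250 patients have been recruited". No rationale, power or interval width accompanies the number.

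Section 3.4 states "The enrolment period is estimated to be 12 months" and then "follow-up up to a minimum of five years, giving total study duration of approximately six years minimum". The Study Summary has the same construction, "12 months enrolment period + up to a minimum of 5 years follow-up for each case", and equates it to roughly 6 years without calling that a minimum.

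Section 1.3 describes the interim analysis completed in December 2014, by which time "220 patients were included across 5 centres between May 2009 and December 2013".

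The visit lists differ. Section 3.4 gives "follow-up intervals of three months, six months, one year, three years, five years" plus an optional seventh year. Section 6 gives "follow-up intervals of three months, one year, three years, five years and an optional seven years". Tables 1 and 2 match Section 6.

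**The concern.** A version dated January 2019 still presents as a forecast an enrolment period that its own background section shows was overrun years earlier. Read literally, the 12 months and the 6 years cannot both stand beside Section 1.3. The 250 is also unconfirmed, because the only count given is 220 and the text never says whether enrolment closed there.

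Three things would be at stake if this reached the analysis. The number implanted is the denominator of the primary endpoint, survival (revision rate), so a shortfall would cost precision. The study duration determines when 5-year and 7-year survival can be read. And Section 9.3 lists a visit outside its window as a protocol deviation and says exclusion is then likely. A visit named in one section only might therefore lead sites to count deviations differently and remove follow-up from the survival analysis.

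**Working it through.** **Inputs.** 250 patients (Section 3.3); 12 months of enrolment (Section 3.4, Study Summary); 5 years of follow-up, optionally 7 (Section 3.4, Table 1); 220 patients from May 2009 to December 2013 (Section 1.3); version date 9 January 2019.

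**1. The plan's own figure.** 12 + 60 = 72 months = 6.0 years. It reproduces, so the fault is an old input and not the sum. With the optional visit, 12 + 84 = 96 months = 8.0 years.

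**2. Enrolment on the reported dates.** Days of the month are not given, so there is a range.
- Shortest: 31 May 2009 to 1 December 2013, 54.0 months.
- Longest: 1 May 2009 to 31 December 2013, 56.0 months.
- Against 12 months: 54/12 = 4.5 times to 56/12 = 4.7 times.

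**3. Duration on the reported dates.**
- To the last 5-year visit: 54/12 + 5 = 9.5 years to 56/12 + 5 = 9.7 years.
- To the optional 7-year visit: 11.5 to 11.7 years.
- These are minima, since any inclusion after December 2013 would lengthen them.

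**4. Accrual.** Observed 220/56 = 3.93 patients per month; planned 250/12 = 20.8. If recruitment had continued at the observed rate (an assumption), the other 30 patients would have needed 30/3.93 = 7.6 months more, and 250 in all 63.6 months.

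**5. What a final size of 220 would cost.** 220/250 = 88%. The interval half-width is 1.96 × √(p(1−p)/n), so it grows by √(250/220) = 1.066. The protocol gives no expected revision rate, so p is an assumed range, with no loss to follow-up:

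| Assumed revision rate | Half-width, n = 250 | Half-width, n = 220 |
|---|---|---|
| 2% | 1.74 points | 1.85 points |
| 3% | 2.11 points | 2.25 points |
| 5% | 2.70 points | 2.88 points |
| 10% | 3.72 points | 3.96 points |

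The largest difference is 3.96 − 3.72 = 0.24 points.

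**6. Whether duration enters the estimate.** Section 6 follows each subject for at least five years after implantation. With staggered entry, survival time runs from each patient's own surgery. Longer accrual moves the calendar date of the last visit and leaves the 5-year estimate as defined. What patients are told in Section 5.2 about the limit of participation, five years or optionally seven, is also per patient and does not depend on the enrolment period.

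**7. Whether a six-month deviation can arise.** Section 9.3 counts visits outside a specified window. Windows appear only in Tables 1 and 2, and neither has a six-month column. Section 3.4 itself refers evaluation to Table 1. There is no six-month window to miss. For a patient included in December 2013, six months ended in about June 2014, some four and a half years before this version.

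**The case for a change.** The best case for a change is that qualifiers such as estimated and minimum cannot protect a figure that was already known to be wrong. The 12 months had been overrun by December 2013 at the latest, and six years from the first inclusion had passed by about May 2015. Section 1.3 is current text and not an amendment log. Either enrolment closed short of 250, in which case Section 3.3 is out of date, or it continued, in which case the timeline is longer still. The two visit lists also disagree on their face.

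Much of that stands. The enrolment period and the Summary's total are contradicted by Section 1.3, the document does not state enrolment status or a final number, and the lists in Section 3.4 and Section 6 need to be reconciled as a matter of editing.

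The statistical consequences do not stand. The 250 is unmet at an interim date, which is different from contradicted. No precision is stated, so none is misstated; the missing rationale for 250 is a separate matter from an outdated timeline. In Section 3.4 the six years is given as a minimum, which a longer study does not falsify. The deviation argument fails because the windows exist only in the tables.

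**Conclusion.** No change to the plan follows. What remains is clerical: an enrolment estimate overtaken by events (54 to 56 months against 12), a total duration that inherits it (at least 9.5 to 9.7 years against about 6), and a visit named in one section with no window or assessments attached. The survival analysis will use the patients actually implanted and their actual dates, whatever the planning paragraphs say. Correcting those paragraphs would alter no data for the reported patients, no estimate and no conclusion.

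This rests on three points. Follow-up is counted per patient from implantation, as Section 6 provides. The tables are the only source of visit windows. And if the final number were 220, which the document does not say, intervals would widen by a factor of 1.066, or at most 0.24 points for assumed revision rates of 2% to 10%.

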4.1. Inclusion Criteria

Subjects meeting all the following criteria will be eligible to be enrolled in the study:

1. Patient is able to understand the meaning of the study and is willing to sign the EC approved, study specific Informed Patient Consent Form.
2. The subject is a male or non-pregnant female between 40 and 75 years of age.
3. The subject requires a primary total knee replacement.
4. Patients with osteoarthritis or posttraumatic arthritis (no rheumatoid arthritis)
5. The subject has intact collateral ligaments.
6. The subject is willing and able to comply with postoperative scheduled clinical and radiographic evaluations and rehabilitation.
7. The subject is capable of understanding the patient scores in the national language.

